4.3.2.2.2 Copy increment from reference method

The copy increment from reference (CIR) method will be applied to impute the post-withdrawal data for any aducanumab-treated subject who withdraws from study early based on data from the placebo group rather than the subject's own randomized treatment group [Carpenter et al. 2013]. Specifically, for a subject on aducanumab high dose (or aducanumab low dose) who withdraws early, his or her mean trajectory after early withdrawal is assumed to be parallel to the mean trajectory of the placebo group, and the difference between the two means is the same as the difference at the time of withdrawal. This method assumes that any benefit gained from previous treatment will be retained, but subjects progress as if they were on placebo after withdrawal from study. For any subject on placebo who withdraws early, his or her post-withdrawal profile will be imputed following the missing-at-random principle. Implementation details can be found in Appendix 6.3.1.

After all missing data have been imputed, an ANCOVA model adjusting treatment group, baseline CDR-SB, baseline MMSE, AD symptomatic medication use at baseline (yes/no), region, and laboratory ApoE ε4 status (carrier/non-carrier) will be applied to analyze the change from baseline CDR-SB.

4.3.2.2.3 Imputation by natural disease progression

Subjects are assumed to exhibit an evolution of the disease similar as the natural disease progression after early withdrawal from study (for all treatment groups). The natural disease progression is determined based on a snapshot of the Alzheimer's Disease Neuroimaging Initiative (ADNI) database [Mueller et al. 2005] obtained in May 2017. A subpopulation was defined that satisfies the major inclusion criteria of Study 221AD302 (and the identically designed Study 221AD301). In this subpopulation, the mean change from baseline CDR-SB at Week 78 is estimated to be about 1.52 for subjects with late mild cognitive impairment (LMCI) and about 2.06 for subjects with mild AD. The missing data at Week 78 for this study will be imputed using the linear extrapolation approach based on subjects' baseline clinical stage (MCI due to AD or mild AD). For example, assuming a mild AD patient whose last non-missing change from baseline CDR-SB measurement is 0.5 at Week 26, the change from baseline CDR-SB at Week 78 for this patient will be imputed as $0.5 + 2.06 * (78 - 26) / 78$, which is 1.87. A similar algorithm will be applied to the MCI patients. After imputation, the change from baseline CDR-SB at Week 78 will be analyzed by an ANCOVA model adjusting treatment group, baseline CDR-SB, baseline MMSE, AD symptomatic medication use at baseline (yes/no), region, and laboratory ApoE ε4 status (carrier/non-carrier).

4.3.2.2.4 Tipping point analysis

The tipping-point analysis is a progressive stress-testing to assess how severe departures from missing-at-random must be in order to overturn the conclusion of the primary analysis [Yan et al. 2009]. For our study, subjects are assumed to have worse scores after early withdrawal from study compared to subjects who remain on study.

The missing data are first imputed by the standard multiple imputation (assuming missing at random). To reflect the worse performance after early withdrawal, pre-specified shift parameters δ_c and δ_t are added to the imputed values for subjects on placebo and aducanumab (include both low dose and high dose), respectively. The adjusted multiple imputed datasets will then be analyzed by an ANCOVA model and the results will be combined using the Rubin's rule for inference.

A range of shift parameters δ_c and δ_t will be applied and p-value will be calculated for each combination of δ_c and δ_t . The tipping region is defined as the combinations of δ_c and δ_t such that the treatment effect is no longer significant (p-value greater than the significance level).

The scientific plausibility of the tipping region will be evaluated. If implausible departures from the missing-at-random assumption (large δ) are needed in order to change the results from statistically significant to insignificant, the results of the primary analysis are considered to be robust to departure from the missing-at-random assumption.

4.3.2.3 Supplementary analysis

4.3.2.3.1 Censoring after intercurrent events

The primary analysis (Section 4.3.2.1) will be repeated with the data censored after any of the following intercurrent events (if multiple events occur to the same subject, data after the earliest event will be censored):

- premature discontinuation of the study treatment;
- any change to concomitant AD symptomatic medications during the study.

The estimate of this analysis reflects the treatment effect of aducanumab if the drug is taken as directed.

4.3.2.3.2 Per-protocol analysis

The per-protocol analysis will be done using the same model as the primary analysis (Section 4.3.2.1) and applying in the per-protocol population (Section 4.1.1).

4.3.2.3.3 Responder analysis

To further assess whether subjects on aducanumab progress differently from those on placebo, responder analysis will be conducted. The responders will be determined by a threshold of the primary endpoint, i.e., subjects whose change from baseline CDR-SB at Week 78 is smaller than or equal to the threshold will be classified as responders and otherwise will be classified as non-responders. All subjects with missing data at Week 78 will be classified as non-responders.

The responder analysis will be conducted for two threshold values: 0.5 or 1.5, i.e., subjects whose change from baseline CDR-SB at Week 78 ≤ 0.5 or ≤ 1.5 . The number of responders

	Statistical Analysis Plan Placebo-Controlled Period	Final V1.0
---	---	-------------------

and the response rate will be summarized by treatment group. The dichotomized response, responder vs. non-responder, will be modeled using a logistic regression with the following covariates: treatment group, baseline CDR-SB, baseline MMSE, AD symptomatic medication use at baseline (yes/no), region, and laboratory ApoE ε4 status (carrier/non-carrier). In addition to the two selected threshold values, the continuous responder curve that displays the percentage of responders under a wide range of threshold values will be presented by treatment group.

Since all missing data will be considered as non-response, which is a special form of missing-not-at-random, this analysis can provide additional insights for the robustness of the primary analysis results.

4.3.2.3.4 Slope analysis

Slope analysis will be conducted to assess the difference between each aducanumab treatment group and placebo in the slope of change from baseline in CDR-SB up to Week 78. A reduction in the slope of the aducanumab treatment group compared with placebo would indicate a slower rate of disease progression, thus reflecting a disease modifying effect of aducanumab. An MMRM model will be used, with dependent variable as the change from baseline CDR-SB score at each visit and with fixed effects of treatment group, time (as a continuous variable), treatment group-by-time interaction, baseline CDR-SB, baseline CDR-SB by time, baseline MMSE, AD symptomatic medication use at baseline (yes/no), region, and laboratory ApoE ε4 status (carrier/non-carrier). The continuous time variable is calculated as number of years since the 1st infusion, so the slope estimate reflects the annual rate of change. The same methods as in the primary analysis will be considered for the covariance structure and the degrees of freedom.

4.3.2.3.5 Divergence effect analysis

A divergence effect analysis will be performed to assess whether the treatment difference between the aducanumab treated patients and the placebo patients increases over time [Li 2017]. A linear trend test will be conducted on treatment difference at Week 26, 50 and 78 estimated from the MMRM model of Section 4.3.2.1, to assess if the slope of the treatment difference is positive or not. Let the estimate of treatment difference be δ_i at time point t_i , where $t_i = 26, 50$ and 78 (week). The least-square estimate of the slope is

$$\beta_{DIF} = \frac{\sum(t_i - \bar{t})\delta_i}{\sum(t_i - \bar{t})^2},$$

where \bar{t} is the mean of t_i 's. The hypothesis to be tested is

$$H_0: \beta_{DIF} \leq 0 \text{ versus } H_a: \beta_{DIF} > 0.$$

Given β_{DIF} is a linear combination of the treatment difference δ_i , this analysis can be implemented by the “estimate” statement in the SAS proc mixed procedure.

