4.3.3.4 Sensitivity/Supplementary analysis

The following sensitivity and supplementary analyses that are planned for the primary efficacy endpoint will also be conducted for the secondary efficacy endpoints:

- Pattern mixture model
- Censoring after intercurrent events
- Per-protocol analysis
- Slope analysis
- Divergence effect analysis

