4.4.2 Amyloid PET SUVR regions-of-interest and reference regions

Amyloid PET standardized uptake value ratio (SUVR) is a quantitative measure of cerebral amyloid plaque burden. The SUVR will be calculated for the following target brain regions-of-interest (ROIs): composite ROI, frontal cortex, parietal cortex, lateral temporal cortex, sensorimotor cortex, anterior cingulate cortex, posterior cingulate cortex, medial temporal cortex, occipital cortex, striatum, and statistical ROI normalized to reference region activity. Additionally, SUVR ROIs including pons and deep subcortical white matter which are believed to be least affected by amyloid pathology will also be evaluated. The composite ROI will comprise of major cortical regions part of the frontal, parietal, lateral temporal, sensorimotor, anterior, posterior cingulate and occipital cortices to serve as a summary measure of global cerebral amyloid burden. The statistical ROI is a region of interest consisting of the posterior cingulate cortex, precuneus and medial frontal cortex that has been demonstrated to yield optimal group separation between subjects with low and high amyloid burden across different reference regions. A negative change from baseline in composite ROI SUVR indicates a reduction in amyloid burden and a negative treatment difference (aducanumab minus placebo) favors aducanumab. The composite ROI will serve as the ROI of primary focus.

The following reference regions will be employed: cerebellum, cerebellum cropped, cerebellar white matter, cerebellar grey matter, deep subcortical white matter, pons, cerebellum + pons, cerebellar white matter + pons, deep subcortical white matter + cerebellum, deep subcortical white matter + pons and deep subcortical white matter + cerebellum + pons. Cerebellum will serve as the reference region of primary focus.

CONFIDENTIAL

The information contained herein may not be used, disclosed, or published without the written consent of Biogen MA Inc.

The composite ROI SUVR using cerebellum as the reference region will be used as the primary endpoint for amyloid PET analysis.

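### The divergence test fixes a positive-slope alternative but gives no sign rule, and no single subtraction order makes that alternative mean benefit on all four endpoints

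*SAP*

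**What the plan says.** SAP Section 4.3.2.3.5 asks whether "the treatment difference between the aducanumab treated patients and the placebo patients increases over time". It takes the treatment differences at Weeks 26, 50 and 78 from the CDR-SB MMRM, computes their least-squares slope, and tests H0: β_DIF ≤ 0 against Ha: β_DIF > 0, "to assess if the slope of the treatment difference is positive or not". The difference itself is introduced only by "Let the estimate of treatment difference be δ_i at time point t_i". No subtraction order is given, and no alpha is given for the one-sided test; Section 4.1 sets a default of two-sided 0.05.

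Section 4.3.3.4 says that certain analyses "planned for the primary efficacy endpoint will also be conducted for the secondary efficacy endpoints", and "Divergence effect analysis" is on its list. Table 2 confirms this for MMSE, ADAS-Cog 13 and ADCS-ADL-MCI and classes the analysis as supplementary. Neither place mentions a change of sign or of alternative.

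On direction of scoring:

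- **CDR-SB.** In the natural-history subpopulation of Section 4.3.2.2.3, "the mean change from baseline CDR-SB at Week 78 is estimated to be about 1.52" for late MCI and about 2.06 for mild AD, so the score rises as the disease advances. Section 4.3.2.3.4 agrees: "A reduction in the slope of the aducanumab treatment group compared with placebo would indicate a slower rate of disease progression".
- **ADCS-ADL-MCI.** Section 4.3.3.3 expects ceiling effects because participants start with little or no impairment. That implies that a higher score is better.
- **ADAS-Cog 13 and MMSE.** The SAP does not state the scoring direction.

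**The concern.** In a one-sided test the sign of the contrast decides what can be concluded. With the wrong sign, a benefit that grows over time cannot be shown, and a widening disadvantage would be reported as a divergence effect. One fixed alternative is here applied to scales that run in opposite directions, with nothing to say how each difference is oriented. If orientation is left to programming, or settled after unblinding, the analysis is no longer pre-specified in the one respect that determines its result.

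**Working it through.** **1. Anchor the scenario.** Section 3 gives a difference of 0.5, SD 1.92, two-sided alpha 0.05, about 90% power, 30% drop-out and 450 per group.

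- n = 2 × (1.960 + 1.282)² × 1.92² / 0.5² ≈ 310 completers per group; 310 / 0.70 ≈ 443, against 450 stated.
- With 450 × 0.70 = 315 completers, power is 0.905, against about 90% stated.

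The plan's figure reproduces, so 0.5 at Week 78 is a fair effect to carry forward.

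**2. Slope weights.** The mean of 26, 50 and 78 is 51.33. The deviations are -25.33, -1.33 and 26.67, and their squares sum to 1354.67. Dividing gives weights of -0.01870, -0.00098 and +0.01969. The printed slope formula is algebraically correct; only the sign of its input is open.

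**3. Apply a growing benefit on CDR-SB.** Assume the benefit is linear from zero to 0.5 at Week 78, so its size is 0.167, 0.321 and 0.500 at the three visits.

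- Aducanumab minus placebo: (-0.01870)(-0.167) + (-0.00098)(-0.321) + (0.01969)(-0.500) = -0.0064 per week (-0.33 per year).
- Placebo minus aducanumab: +0.0064 per week.

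**4. Chance of accepting Ha: β_DIF > 0.** The Week 78 SD is 1.92. The Week 50 SD is taken as the one-year value, 1.92 / 1.39 = 1.38. The remaining inputs are assumptions: Week 26 SD 0.8 to 1.2, common correlation 0.4 to 0.8, 315 or 374.5 (535 × 0.70) completers per group, one-sided alpha 0.05 or 0.025.

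| Order on CDR-SB | Expected slope per week | Probability of accepting Ha |
|---|---|---|
| Aducanumab minus placebo | -0.0064 | below 0.0001 (one-sided p at the expected slope about 0.989 or higher) |
| Placebo minus aducanumab | +0.0064 | 0.63 to 0.98 |

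The unstated alpha matters too. With Week 26 SD 1.0, correlation 0.6 and 315 per group, the correctly oriented test has probability 0.850 at one-sided 0.05 and 0.764 at 0.025.

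**5. All four endpoints.** What a positive slope means under each fixed order (ADAS-Cog 13 and MMSE under standard scoring):

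| Endpoint | Aducanumab minus placebo | Placebo minus aducanumab |
|---|---|---|
| CDR-SB | growing harm | growing benefit |
| ADAS-Cog 13 | growing harm | growing benefit |
| MMSE | growing benefit | growing harm |
| ADCS-ADL-MCI | growing benefit | growing harm |

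The CDR-SB and ADCS-ADL-MCI rows rest on the SAP's own text and are enough to show that no single order serves every endpoint.

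**The case against.** A reader might infer something stronger: that the SAP's own sign convention makes the primary-endpoint test a test for harm. The pointers are that Section 4.4.2 says "a negative treatment difference (aducanumab minus placebo) favors aducanumab", that the imputation formula in Appendix 6.3.1 subtracts the placebo mean from the treatment mean, and that Section 4.3.2.3.5 names aducanumab first. The document does not support that inference. The wording in Section 4.4.2 concerns amyloid PET SUVR only, the appendix formula is an imputation step, and neither sets the sign of this test. Where the SAP gives the CDR-SB effect a direction, positive is benefit: Section 3 writes the planned benefit as 0.5, and the conditional power in Section 5 counts a large positive Z as favouring aducanumab. On that orientation β_DIF > 0 is the right alternative for CDR-SB.

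It can also be argued that Section 4.3.3.4 only lists analyses to be adapted. The divergence section refers to the CDR-SB model, so the secondary endpoints must in any case use their own models, and a sensible analyst would orient each difference towards benefit. The method is also cited to a publication that may settle the sign but cannot be checked here.

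These arguments remove the claim that the CDR-SB test is necessarily reversed. They do not supply the missing rule. The cues within the SAP conflict, and the adaptation is left to the analyst.

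**Conclusion.** The point stands as an undefined sign combined with a one-sided alternative that, under any single subtraction order, points to harm on two of the four endpoints. Whether the primary endpoint is among those two depends on which order is taken, and the SAP leaves that open. The sign results need only the scoring directions; those of ADAS-Cog 13 and MMSE are assumed standard. The acceptance probabilities rest further on linear divergence and on the assumed SDs and correlations. Severity is minor to moderate: the analysis is supplementary, Section 4.3.1 gives such analyses no multiplicity adjustment, and neither the primary test, the confirmatory sequence nor the futility rule depends on it.

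**What to change.** In Section 4.3.2.3.5, define δ_i for each endpoint so that a positive value favours aducanumab: placebo minus aducanumab for CDR-SB and ADAS-Cog 13, aducanumab minus placebo for MMSE and ADCS-ADL-MCI. Refer to that definition from Section 4.3.3.4. Then either keep Ha: β_DIF > 0 and state its one-sided alpha, or test two-sided at 0.05 in line with Section 4.1. In both cases report the signed slope with its confidence interval. The cost is about one sentence of SAP text and the sign of a contrast in the SAS ESTIMATE statement. Sample size and data collection are unaffected. The change should be made before unblinding.

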4.3.2.4 CDR subscores and CDR global score

The CDR is comprised of 6 domains: Memory, Orientation, Judgment and Problem Solving, Community Affairs, Home and Hobbies, and Personal Care. CDR-SB is the sum of the scores

CONFIDENTIAL

The information contained herein may not be used, disclosed, or published without the written consent of Biogen MA Inc.

for these 6 domains. In addition, two CDR subscores have been proposed [Tractenberg 2005]: a “cognitive” subscore equaling the sum of the Memory, Orientation, and Judgment and Problem Solving box scores, and a “functional” subscore equaling the sum of Community Affairs, Home and Hobbies and Personal Care box scores. For each of the 6 box scores, and the CDR cognitive subscore and CDR functional subscore, the baseline value and the change from baseline at each post-baseline visit will be summarized by treatment group. The same MMRM model as the primary analysis will also be applied to the CDR cognitive subscore and CDR functional subscore.

The CDR global score is a composite score obtained by combining the 6 box scores using a scoring algorithm that weights memory as the primary domain and all other domains as secondary [Morris 1993]. The distribution of CDR global score will be summarized (as a categorical variable) by treatment group at each post-baseline visit.

4.3.3 Secondary Efficacy Endpoints

4.3.3.1 Primary analysis of MMSE

The change from baseline MMSE scores will be summarized by treatment group at each post-baseline visit. An MMRM model will be used as the primary analysis to analyze change from baseline MMSE using fixed effects of treatment group, time (categorical), treatment group-by-time interaction, baseline MMSE value, baseline MMSE by time interaction, AD symptomatic medication use at baseline (yes/no), region, and laboratory ApoE ϵ 4 status (carrier/non-carrier). The same methods as in the primary analysis will be considered for the covariance structure and the degrees of freedom.

4.3.3.2 Primary analysis of ADAS-Cog 13

The change from baseline ADAS-Cog 13 scores will be summarized by treatment group at each post-baseline visit. An MMRM model will be used as the primary analysis to analyze change from baseline ADAS-Cog 13 using fixed effects of treatment group, time (categorical), treatment group-by-time interaction, baseline ADAS-Cog 13, baseline ADAS-Cog 13 by time interaction, baseline MMSE, AD symptomatic medication use at baseline (yes/no), region, and laboratory ApoE ϵ 4 status (carrier/non-carrier). The same methods as in the primary analysis will be considered for the covariance structure and the degrees of freedom.

4.3.3.3 Primary analysis of ADCS-ADL-MCI

The change from baseline ADCS-ADL-MCI scores will be summarized by treatment group at each post-baseline visit. An MMRM model will be used as the primary analysis to analyze change from baseline ADCS-ADL-MCI using fixed effects of treatment group, time (categorical), treatment group-by-time interaction, baseline ADCS-ADL-MCI, baseline ADCS-ADL-MCI by time interaction, baseline MMSE, AD symptomatic medication use at baseline (yes/no), region, and laboratory ApoE ϵ 4 status (carrier/non-carrier). The same methods as in the primary analysis will be considered for the covariance structure and the degrees of freedom.

The primary analysis of ADCS-ADL-MCI will use the pooled data from both Studies 221AD301 and 221AD302 (analysis for each individual study will also be performed). Pooled data will be used for the primary analysis because functional outcomes are expected to be less sensitive to change within the study duration than cognition measures due to ceiling effects [Rockwood 2007], as subjects entering the study will have no or little measurable impairment at baseline. It has also been observed in previous studies of more impaired patients (mild to moderate/severe) that functional outcome treatment effect sizes are small [Hansen 2007].

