1.2 Secondary Objectives and Endpoints

The secondary objectives of this study are:

- To assess the effect of monthly doses of aducanumab as compared with placebo on clinical progression as measured by the Mini-Mental State Examination (MMSE).
- To assess the effect of monthly doses of aducanumab as compared with placebo on clinical progression as measured by Alzheimer's Disease Assessment Scale-Cognitive Subscales (13 items) [ADAS-Cog 13].
- To assess the effect of monthly doses of aducanumab as compared with placebo on clinical progression as measured by Alzheimer's Disease Cooperative Study-Activities of Daily Living Inventory (Mild Cognitive Impairment version) [ADCS-ADL-MCI].

The secondary endpoints are:

- Change from baseline in MMSE score at Week 78.
- Change from baseline in ADAS-Cog 13 score at Week 78.
- Change from baseline in ADCS-ADL-MCI score at Week 78.

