The same imputation algorithm will be applied to CDR-SB and MMSE, if only 1 box (of 6) of CDR is missing or if only 2 or fewer items (out of 11) are missing for MMSE. If the score from more than 1 box of CDR or more than 2 items of MMSE is not available, the CDR-SB or MMSE at that visit will be considered missing.

The total score of the tertiary endpoint NPI-10 will be imputed using the same prorating principle if only 1 item (out of 10) is missing. For EQ-5D and mPDQ-20, if any item is missing, any total or sum involving that item will be considered missing.

Considerations for multiple comparison adjustments

A sequential (closed) testing procedure will be used to control the overall Type I error rate due to multiple comparisons for the primary endpoint. The order of treatment comparisons is as follows: aducanumab high-dose versus placebo and aducanumab low-dose versus placebo. All comparisons after the initial comparison with $p > 0.05$ will not be considered statistically significant.

Secondary endpoints have been rank prioritized, in the order shown in Section 1.2. In order to control for a Type I error for the secondary endpoints, a sequential closed testing procedure will be used and will include both the order of the secondary endpoints and treatment comparisons. Specifically, for each of the secondary endpoints, a sequential (closed) testing procedure, as for the primary endpoint, will be used to control the overall Type I error rate due to multiple treatment comparisons. If statistical significance is not achieved for 1 or 2 treatment comparisons, all endpoint(s) of a lower rank will not be considered statistically significant for that 1 or 2 treatment comparisons, respectively.

There will be no multiple comparison adjustments for the sensitivity and supplementary analyses for the primary and secondary efficacy endpoints, the tertiary efficacy endpoints, the subgroup analyses or the additional analyses.

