4.4.5 Correlation between amyloid PET and CDR sum of boxes

Pearson and Spearman correlation

Pearson and Spearman correlations between change from baseline amyloid PET composite ROI using cerebellum as reference region at Week 78 and change from baseline CDR-SB at Week 78 will be conducted by treatment groups (placebo, low dose and high dose, and active total) in the ¹⁸F-florbetapir amyloid PET analysis population. Pearson and Spearman partial correlations adjusting for baseline amyloid PET composite ROI and baseline CDR-SB will also be conducted by treatment groups at Week 78. The estimated correlation coefficients, p-values and the 95% confidence intervals will be provided. Given that reductions in cerebral β -amyloid ($A\beta$) content may precede clinical effects (e.g., slowing of clinical decline), Pearson and Spearman correlations and partial correlations between change from baseline amyloid PET composite ROI at Week 26 and change from baseline CDR-SB at Week 78 will also be conducted.

Correlation analysis will be done on each individual study as well as in the pooled data of the 221AD301 and 221AD302 studies. The correlation analysis based on the pooled data will be considered as the primary analysis.

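### The pooled 301+302 ADCS-ADL-MCI model and the pooled PET/CDR-SB correlation carry no study term, and a significant pooled ADCS-ADL-MCI result supports a cross-study conclusion, not a 302-specific one

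*SAP*

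**What the plan says.** All references are to the placebo-controlled SAP.

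- **Endpoint and rank.** Section 1.2 lists "Change from baseline in ADCS-ADL-MCI score at Week 78" as the last of three secondary endpoints, after MMSE and ADAS-Cog 13. Section 4.3.1 says: "Secondary endpoints have been rank prioritized, in the order shown in Section 1.2".
- **Gate.** The same section adds: "If statistical significance is not achieved for 1 or 2 treatment comparisons, all endpoint(s) of a lower rank will not be considered statistically significant", applied to the comparison that failed.
- **Data set.** Section 4.3.3.3 says: "The primary analysis of ADCS-ADL-MCI will use the pooled data from both Studies 221AD301 and 221AD302". It adds in brackets that "analysis for each individual study will also be performed". Sections 4.3.3.1 and 4.3.3.2 contain no pooling provision for MMSE or ADAS-Cog 13.
- **Model.** The ADCS-ADL-MCI model is fitted "using fixed effects of treatment group, time (categorical), treatment group-by-time interaction, baseline ADCS-ADL-MCI, baseline ADCS-ADL-MCI by time interaction", and then "baseline MMSE, AD symptomatic medication use at baseline (yes/no), region, and laboratory ApoE" status. Neither study nor treatment-by-study is listed.
- **Correlation.** Section 4.4.5 plans PET/CDR-SB correlations per study and pooled, and says: "The correlation analysis based on the pooled data will be considered as the primary analysis". The partial correlations adjust for baseline PET and baseline CDR-SB, not for study.
- **Reason for pooling.** Section 4.3.3.3 expects functional outcomes to be less sensitive than cognitive ones because of ceiling effects, and notes small functional effect sizes in earlier studies.

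**The concern.** Studies 301 and 302 are separate trials, so randomisation protects the comparison within each one. A pooled model would normally carry that structure as a study effect. Without it, any difference between the trials in average ADL decline that the listed covariates do not explain is treated as noise. In a pooled correlation, a difference between the trials in mean PET change and mean CDR-SB change can look like an association between subjects.

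The second matter is interpretation. MMSE and ADAS-Cog 13 are tested in 302. The next test in the sequence uses both trials, so it answers a different question from the tests that gate it. The SAP does not say how a significant third-ranked result is to be worded. Reported as a finding of Study 302, it could overstate what 302 itself shows.

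**Working it through.** **1. The plan's own figure.** The SAP gives no effect, SD or power for ADCS-ADL-MCI. Its only power statement (Section 3) is for CDR-SB: difference 0.5, SD 1.92, two-sided 0.05, 90% power, 30% drop-out, 450 per group.

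n = 2 × (1.960 + 1.282)² × 1.92² / 0.5² ≈ 310 evaluable per group; 310 / 0.70 ≈ 443.

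This agrees with 450 to within 2%. The 90% level is used below only as a benchmark for a study that could detect its own effect.

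**2. Missing study term in the MMRM.** Assume equal study sizes, the same allocation and a between-study shift of d residual SDs after the listed covariates. Splitting subjects half and half between the studies adds d²/4 to the residual variance, so the standard error is multiplied by √(1 + d²/4).

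| d | Factor | SE inflation |
|---|---|---|
| 0.2 | √1.0100 = 1.0050 | 0.5% |
| 0.5 | √1.0625 = 1.0308 | 3.1% |

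Treatment is balanced within each study, so the treatment estimate is not biased.

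**3. Missing study term in the correlation.** Assume equal numbers per study, no within-study correlation, and mean shifts between studies of a SDs in PET change and b SDs in CDR-SB change. The pooled Pearson correlation is then (ab/4) / √[(1 + a²/4)(1 + b²/4)].

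- a = b = 0.2: 0.01 / 1.01 = 0.010
- a = b = 0.5: 0.0625 / 1.0625 = 0.059

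The sign follows the directions of the shifts, so a real correlation can be raised or lowered by a similar amount.

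**4. What the pooled ADL test says about 302.** With equal information, Z(pooled) = (Z302 + Z301)/√2. An effect with 90% stand-alone power has mean Z = 1.960 + 1.282 = 3.242. If only one study has such an effect:

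- Mean pooled Z = 3.242 / √2 = 2.292
- P(Z > 1.960) = Φ(0.332) = 0.63

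With 80% stand-alone power the figures are 2.802 / √2 = 1.981 and 0.51.

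By symmetry this covers both cases. With no ADL effect in 302 and a 90%-power effect in 301, the pooled test rejects in favour of aducanumab 63% of the time. A 302 effect with 90% power alone keeps 63% if 301 has none. In simulation of the second case, 302 alone was significant and the pooled test was not in 28% of trials. As an illustration, Z302 = 2.5 (p = 0.012) with Z301 = 0 gives pooled Z = 1.77, p = 0.077.

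These are rejection probabilities of the pooled test taken by itself. They do not multiply in the chance of reaching it, nor allow for correlation between endpoints.

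**5. Does a study term change step 4?** A simulation with no effect in 302, a 90%-power effect in 301 and a 0.2 SD shift between studies gave pooled rejection of about 62% without a study main effect and 63% with it. The dependence on 301 comes from pooling, not from the missing term.

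**The case against.** Three stronger readings are tempting, and the SAP does not support them.

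**That the missing study term lets 301 decide 302's result.** Step 5 shows that the term makes almost no difference to this. Section 3 calls 301 identically designed, so with the same 1:1:1 allocation the omission does not confound treatment either.

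**That 302's sequence has a 63% false-positive rate.** It does not. Under Section 4.3.1, ADCS-ADL-MCI counts for a dose only after MMSE and ADAS-Cog 13 are significant for that dose, and those are 302-only tests. If 302 has no effect on any of the three, the MMSE gate alone caps a claim in favour of aducanumab at 2.5% for that dose. The 63% needs real cognitive effects in 302, no ADL effect there, and a substantial ADL effect in 301. If neither study has an ADL effect, the pooled test holds its 0.05 level. The gate does not guard against dilution of a real 302 effect.

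**That the hierarchy test must be 302 only.** Section 4.3.3.3 pre-specifies pooling and gives a reason. If the effect is common to both trials, power becomes Φ(√2 × (1.960 + z) − 1.960), where z is the normal quantile of the stand-alone power. Stand-alone powers of 30%, 50%, 60% and 80% then become 53%, 79%, 88% and 98%. That is a substantial gain for an insensitive endpoint, and the per-study result is reported as well. The choice is a trade-off.

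Two further points stand. The SAP does not say outright that the pooled p-value is the one entered at rank three; that is inferred from its being called the primary analysis. The PET correlation is a tertiary analysis outside the hierarchy and is also run per study, so less depends on it.

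**Conclusion.** The point holds as a small modelling omission plus a matter of wording. Both pooled primary analyses lack a study term. For the MMRM the cost is a little precision: 0.5% in standard error at a 0.2 SD shift and 3.1% at 0.5 SD, without bias in the treatment comparison. For the correlation, shifts of the same sizes in both variables would add about 0.01 to 0.06 to a null correlation. These figures assume equal study sizes, and the SAP does not give the actual shifts.

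A significant pooled ADCS-ADL-MCI result is evidence about the two trials together. Read as a statement about 302 alone, it can mislead in either direction, by the amounts in step 4 under equal information. Unequal completion would change those percentages but not the conclusion. Nothing here shows that pooling is wrong or that Type I error is uncontrolled under the joint null.

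**What to change.** 1. In Section 4.3.3.3, add study and study-by-time as fixed effects to the pooled ADCS-ADL-MCI model. With three post-baseline visits this uses three degrees of freedom.
2. Report the treatment-by-study estimate at Week 78 for each dose, with its 95% confidence interval, beside the per-study results already planned. This is descriptive and not a further gate.
3. In Section 4.4.5, partial study out of the pooled Pearson and Spearman correlations, adding it to the baseline adjustments where those are used.
4. In Sections 4.3.1 and 4.3.3.3, state that the pooled result is the one tested at rank three, if that is the intention, and that significance there is reported as a cross-study conclusion from 301 and 302.

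The cost is SAP wording and one extra model term, with no new data and no material loss of power. Replacing the pooled test by the 302-only test is not part of this change. It would give up power if the effect is small and common to both trials, and that choice is the sponsor's to weigh.
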